Those who enroll in March 2023 will have baseline labs in March 2023 and final labs in June 2023 (3 months later). This is due to the end of study funding in June 2023. This is further specified in Section IV, Table 4 below.

Testing for calcium, PTH, and vitamin D will be done at UCM (UCMC, River East, or Ingalls) or Rush ([name]'s lab), with the site for each subject selected based on which site is most convenient for the subject. Vitamin A, which will be drawn only from UCM subjects, will be sent to an outside lab for analysis. Throughout the study period we will tell subjects about calcium, PTH and vitamin D lab results only if they suggest a safety concern for which we would like them to seek care from a medical professional. Except in the instance of a safety concern, subjects will be blinded to their vitamin A & D levels, calcium and PTH throughout the study to ensure protocol compliance. At the end of their time in the study, we will provide test results to subjects as indicated in "Study Completion Email V4". At the end of the intervention period for all participants in this protocol, we will unblind participants to their vitamin D dose assignment as indicated in "Dose Unblinding Email V1". We will do this at the end of the intervention for all participants because we, as the study team, are also currently blinded to dose assignments until the end of the intervention period for all participants. For participants who transition to participate in protocol 20-0847, unblinding will occur at the end of the intervention period for all participants in that study. Blood draws for COVID-19 antibodies will also occur at same location as their other lab draws for convenience, consolidated with other labs, but antibody testing will occur at UCM using the Roche assay for consistency given the differing ranges of different COVID-19 assays. Subjects will be instructed during the consent process to seek COVID-19 PCR testing on their own at a site convenient for them if they become symptomatic or were exposed to COVID-19, which is aligned with recommendations from CDC and IDPH. COVID-19 PCR tests will not be part of the research labs, and thus will not be paid for by the study. Subjects will self-report positive COVID-19 PCR results in the quarterly survey. Laboratory records will be monitored regularly by site PIs, Co-Investigators, and members of the DSMB and Clinical Advisory Committee for safety. Patient-reported outcome measures will be measured by a RedCap-based survey.

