**Table 5: Monitoring timeline**

*Any dates specified after June 2022 are contingent on granting of second no-cost extension in Spring 2022*

Date	Activity	Description
September 2020	Clinical Advisory Committee meeting	9 faculty members of the CAC meet to create guidelines for safety testing and cutoffs, and to create the exclusion criteria
February 2021	Clinical Advisory Committee meeting	Faculty members of the CAC meet to review preliminary testing data and any clinical concerns. Will also discuss strategies for recruitment of healthy volunteers
June 2021	DSMB first meeting	DSMB meet with the PI and analysts to discuss study aims, outcomes, survey

		instruments, testing measurements, and data requests
August 2021	DSMB second meeting	DSMB meet to ensure randomization has worked: review of baseline testing and demographic characteristics by arm and review of subject complaints
December 2021	DSMB interim efficacy analysis (closed meeting)	DSMB will review longitudinal testing data by arm and conduct an interim efficacy analysis
May 2022	DSMB meeting	DSMB will meet to review trst results and PRO measurements aligned with the aims
January 2023	DSMB meeting	DSMB will meet to review test results and PRO measurements aligned with the aims.
May 2023	Final DSMB meeting	DSMB will meet to review test results and PRO measurements aligned with the aims. Will discuss dissemination strategies

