The sample size was chosen to have at least 80% power to detect a 25% or larger decrease in the hazard of developing COVID-19 between study arms at  $p<0.05$  assuming a 30% baseline COVID-19 incidence rate over the study period, in line with the 3% per month incidence cited above.

*Individuals are eligible to enroll in the study if they:*

1. Are 18 years or older.
2. Live or work in the Chicagoland area (Illinois counties: Cook, Lake, McHenry, DuPage, Kane, Kendall, Grundy, Will, and Kankakee; Indiana counties: Lake and Porter).
3. Are interested in vitamin D as a potential preventive measure against COVID-19 in which they self-administer a daily dose of vitamin D during the 9-month study period.
4. Are willing to attend the laboratory for drop-in appointments at UChicago Medicine, Ingalls Hospital, or Rush University Medical Center every 3 months at up to 4 time points over up to a 9-month period for blood draws measuring COVID-19 antibodies, calcium, vitamin D and PTH levels.
5. Are willing to complete self-report measures at up to 4 time points over the course of up to 9 months by completing a 15-minute survey at intake by telephone or via web and 10-minute web-based follow-up surveys.

*Individuals are excluded from the study if they:*

1. Report being pregnant, planning to become pregnant, and/or report breastfeeding during the study period.
2. Report a history of chronic kidney disease, including a history of abnormal GFR and/or creatinine.
3. Report a history of hyperparathyroidism.
4. Report a history of increased falls.
5. Report a history of hypercalcemia.
6. Report a history of gastrointestinal absorptive disorders, including having undergone bariatric surgery.
7. Report a history of kidney stones (1 in past year or 2 in lifetime).

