For our primary outcome of COVID-19 infection as measured by patient report of clinically confirmed COVID-19 (or viral PCR when available) and secondary outcomes of COVID-19 antibody seroconversion and disease severity (hospitalization, ICU stay, ventilator use, death), hazard models will be employed to assess the effect of each vitamin D dosing strategy on the outcome. We will first develop hazard ratios for between-group analyses on the primary outcome using log-rank tests, and then develop Cox proportional hazard models to model the hazard function on a set of covariates including but not limited to, moderate or high vitamin D dose, baseline vitamin D levels, age, gender, race, ethnicity, sun exposure, sleep habits, exposure of cohabitants, job type, and study site. We will also control for randomization date to adjust the underlying hazard function for COVID-19 prevalence over time. While our primary analysis will pool subjects randomized to either the moderate or high dose and compare them to low dose subjects, we will also perform secondary analyses comparing low to moderate and low to high and additional analyses that use post randomization vitamin D levels as time varying covariates. The design thus seeks to maximize potential to find statistically significant results between different dosages given uncertainty in subject willingness to be randomized to different doses. As noted above, the sample size was chosen to have at least 80% power to detect a 25% or larger decrease in the hazard of developing COVID-19 between study arms at  $p<0.05$  assuming a 30% baseline 10-month COVID incidence over the study period, in line with the 3% monthly incidence cited above. As finding that a higher dose has no effect or a paradoxical adverse effect on COVID incidence would both lead to use of a lower dose given even the small risks of higher dose vitamin D, Ruxson and Neuhauser would argue for use of a 1-sided test, resulting in 80% power to detect a 20% or larger decrease.

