## XI. Monitoring of safety

The current study represents a multi-site clinical trial in which the risks inherent to the intervention are of minimal risk to participants given the long-standing use of vitamin D supplementation with few adverse events. The protocol's exclusion criteria and monitoring plan limit the likelihood that subjects will develop a severe medical condition during the course of this study. Commensurate with these risks, the PI [name], with support from the Clinical Advisory Committee and co-investigators Drs. [name], [name], [name], and [name], will conduct regularly monitoring of safety which will be overseen by a formal Data and Safety Monitoring Board (DSMB). The independent DSMB will be comprised of three experts, a Chair and two members, who will provide regular oversight for this multi-site study. The PI has already identified all three DSMB members, one of whom will be the Chair. These individuals are senior faculty members and hold expertise in clinical trial oversight and design, biostatistics, endocrinology, pulmonology and critical care medicine.

The protocol's safety and monitoring guidelines as described below have been created in collaboration with the already-identified members of the Clinical Advisory Committee, a committee of interdisciplinary clinicians who will provide the PI clinical support and guidance. If funded, the protocol will be overseen by the DSMB which will provide continued guidance on administration of the study protocol and management of any adverse events. The DSMB will work closely with the PI, co-investigators, and Clinical Advisory Committee, monitoring the intervention on an ongoing basis and meeting quarterly to review intervention data and provide recommendations as needed for modifying the intervention. Study analysts will work with the PI and Co-Investigators to send laboratory data to the DSMB regularly for review.

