### [Monitoring of the intervention](#)

To monitor for toxicity, calcium levels will be checked at study initiation to assess for baseline hypercalcemia and at each subsequent blood draw (3, 6, and 9 months) to monitor for incidental or study-induced hypercalcemia. If study participants are found to be hypercalcemic, they will be told to cease vitamin D supplementation. For UCM patients with a calcium level 10.5-12 mg/dL and for Rush patients with a calcium level of 11.3-12mg/dL, patients will be instructed to consult with their primary care physician. For patients with a calcium level of 12.1-14 mg/dL, patients will be referred to urgent care. For patients with a calcium level greater than 14 mg/dL, patients will be referred to the emergency room. These participants will continue to undergo monitoring blood draws and surveys and may resume vitamin D supplementation per study protocol with a physician note. Based on conversations with our Clinical Advisory Board and prior studies, we expect very few people to become hypercalcemic due to study medication. The DSMB will also conduct an interim analysis of COVID-19 incidence among the two study arms approximately 6 months into the study to determine study continuation in addition to routine safety review.

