### Monitoring Frequency

The DSMB will meet to review initial laboratory values and quarterly thereafter to review the overall protocol administration, review adverse events, and trends in laboratory values for determination of safe progression of the study. DSMB members will schedule additional meetings as needed to review adverse events. In addition to these quarterly meetings, Board members, along with the PI and Co-Investigators, will receive regular data reports from phlebotomy with all subjects' laboratory values, with higher values indicated. Board members will keep in close contact with the PI and Co-Investigators to refer individual patients to seek outside care for high laboratory values, in addition to the resources provided to subjects to seek care, such as an on-call pager for primary care.

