### Summary of Consent Form Versions

**For those consented March 31 2022-December 31, 2022:** We will use consent form Version 10 (UCMC) or Version 11 (Ingalls), both in English and Spanish. This is because these consent forms are written for those who participate in the study for 6-9 months. Subjects who consent before October 1, 2022 will be in the study for 9 months. Subjects who consent on or after October 1, 2022 will be in the study for 6 months. This information is also clarified in these consent forms and in Table 3 of Section IV above. Version 10, like Version 8, has language for opt-in labs while Version 11 does not. We will use consent form Version 4 for Rush subjects.

For those who consented using UCM Consent Version 8 or 9, or Rush Consent Version 3 (thus who consented on or after January 1, 2022 and in follow up for less than 6 months), we wish to allow for the option to re-consent these subjects on UCM Consent Version 10 or 11, or Rush Consent Version 4, to allow these subjects to participate in the study for a full 9-month period (and would thus receive 4 total blood tests and 4 follow-up

surveys). This re-consent is entirely voluntary. If these subjects do not wish to re-consent, they will end their time in the study June 30, 2022.

**For those consented January 2023-March 31, 2023:** We will use consent form Version 12 (UCMC) or Version 13 (Ingalls), both in English and Spanish. With the removal of the final PTH lab approved in Amendment 54, we will then use consent form Version 14 (UCMA) or Version 15 (Ingalls), both in English and Spanish. This is because these consent forms are written for those who participate in the study for less than 6 months. This information is also clarified in these consent forms and in Table 4 of Section IV above. Version 12 and 14, like Versions 8 and 10, have language for opt-in labs while Version 13 and 15 do not.

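### The plan has an interim efficacy comparison but no rule for acting on it, and the only efficacy significance level is an unadjusted 0.05

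*Combined protocol and SAP*

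**What the plan says.** Two places in the combined protocol and SAP describe one interim comparison. Section XI (Monitoring of the intervention) plans an "interim analysis of COVID-19 incidence among the two study arms approximately 6 months into the study to determine study continuation" and sets this apart from the usual review of safety. Table 5 in Section IV enters it for December 2021 as a closed meeting: "DSMB will review longitudinal testing data by arm and conduct an interim efficacy analysis". COVID-19 infection is the primary outcome in Section IX.

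The only significance level attached to efficacy is p<0.05. It stands in the sample-size statement of Section VIII, "at least 80% power to detect a 25% or larger decrease in the hazard of developing COVID-19 between study arms", and again in Section IX, with no side given. The other p<0.05 in Section IX concerns the proportional hazards check.

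The remaining text on the DSMB gives no efficacy rule. Section XI describes the board as "meeting quarterly to review intervention data and provide recommendations as needed for modifying the intervention". The charter (Section XII, Monitoring Frequency) has it meet to "review the overall protocol administration, review adverse events, and trends in laboratory values for determination of safe progression of the study", and does not mention the interim efficacy look.

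On sidedness, Section IX repeats the 25% design claim and then says that an outside argument "would argue for use of a 1-sided test, resulting in 80% power to detect a 20% or larger decrease". It neither adopts nor rejects that argument.

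**The concern.** The look compares the primary outcome by arm, is labelled an efficacy analysis, is kept apart from safety review and can affect whether the trial continues. A reader who asks what p value would have justified stopping for benefit finds only 0.05. Using that level at both the interim look and the final analysis gives a false claim of benefit or harm two chances to occur, so the error rate is no longer 5%. The plan also does not exclude a claim of benefit at the look. The error rate of the primary result therefore cannot be worked out from the document.

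There is a smaller gap of the same kind at the end of the trial. No sentence says whether the pooled comparison is judged one- or two-sided, so a narrow band of results could be called either success or failure.

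**Working it through.** **1. The plan's own power figures.** Inputs from Sections III, VIII and IX: 2,000 participants, 1:1, 30% control risk over 10 months, no loss.
- Expected events D = 1,000 × 0.30 + 1,000 × (1 − 0.70^HR).
- Power = Φ(√D/2 × |ln HR| − z), with z = 1.960 (two-sided 0.05) or 1.645 (one-sided 0.05).
- HR 0.75: D = 300 + 234.7 = 534.7, and √D/2 × |ln HR| = 3.326. Two-sided power is Φ(3.326 − 1.960) = 91.4%.
- HR 0.80: D = 300 + 248.2 = 548.2, and √D/2 × |ln HR| = 2.612. One-sided power is Φ(2.612 − 1.645) = 83.3%. Two-sided power is Φ(2.612 − 1.960) = 74.3%.

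On the stated inputs, the 25% claim of at least 80% power holds two-sided. The 20% figure holds one-sided, as the plan labels it.

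**2. Overall error with two looks.** Let Z1 and Z2 be the interim and final test statistics and t the fraction of final events available at the interim. Under no effect they are bivariate normal with correlation √t. Overall error = 1 − P(|Z1| < c1 and |Z2| < c2). The documents give no t, so the range is shown.

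| Assumed t | Two-sided 0.05 at both looks (c1 = c2 = 1.960) | Interim two-sided 0.001 (c1 = 3.291), final 0.05 (c2 = 1.960) |
|---|---|---|
| 0.10 | 9.5% | 5.1% |
| 0.25 | 9.1% | 5.1% |
| 0.50 | 8.3% | 5.0% |
| 0.75 | 7.3% | 5.0% |
| 0.90 | 6.5% | 5.0% |

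The middle column applies only if the look could support a claim at nominal 0.05. If it could stop the trial only for harm or futility, a claim of benefit can arise only at the end and the error does not exceed 5%.

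**3. Power cost of the p<0.001 rule.** The final test stays at 0.05, so the rule only adds ways to reject and power cannot fall. At HR 0.75 and t = 0.5, power is 91.4% with or without the look.

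**4. The sidedness band.** The largest observed hazard ratio that reaches significance is exp(−2z/√D). With D = 548:
- two-sided: exp(−2 × 1.960/√548.2) = 0.846;
- one-sided: exp(−2 × 1.645/√548.2) = 0.869.

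An observed hazard ratio between 0.846 and 0.869 passes one test and fails the other.

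**The case against.** The strongest reply is that the inflation is conditional. A reader might infer that the trial runs at 8.3% error. The documents do not support that. They do not say that the look could yield a claim of benefit, nor that it would use 0.05. Determining continuation, in a section on safety monitoring, also fits stopping for harm or futility. This stands, so the size is given only as a conditional figure. It does not remove the gap: Table 5 calls the look an efficacy analysis, and nothing limits its use.

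A reader might also count every DSMB meeting as a further efficacy look. The text does not bear that out. The charter lists conduct, adverse events and laboratory trends, and only the December 2021 entry in Table 5 is called an efficacy analysis.

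On sidedness, a reader might infer that the plan has moved to a one-sided test or overstates its power. Neither holds. Setting the one-sided 20% figure against the 25% claim makes sense only if the 25% claim is two-sided, and both figures reproduce. What remains is one missing sentence.

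Finally, the look may already be past. Section XIV contains later text ("With the removal of the final PTH lab approved in Amendment 54"), which suggests this but does not show that the look was held. If it was, a boundary chosen now cannot be called prespecified. That stands, and the fix is split accordingly.

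**Conclusion.** The point holds as a gap that should be fixed. One efficacy comparison by arm is planned to inform continuation, and the plan has no rule for acting on it beyond an unadjusted 0.05. If the look could support a claim of benefit at two-sided 0.05, overall error is about 8.3% at half of the information and 6.5% to 9.5% over fractions of 90% down to 10%. These figures rest on the assumed fraction, on a single interim look and on that use of it. If the look could stop the trial only for harm or futility, there is no excess error. The documents do not settle which applies.

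Sidedness is minor. It does not inflate error in itself, and it matters only for observed hazard ratios of about 0.846 to 0.869 at 548 events. The sample-size claim is not in question.

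**What to change.** **If the look has not taken place:** state in Section IX and in the DSMB charter that it can support a claim of benefit only at two-sided p<0.001, with the final pooled comparison at two-sided 0.05.

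**If the look has taken place:** report the rule actually applied, or that none was set. Do not present a later boundary as prespecified. Report the final test with the look disclosed.

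**In either case:** add one sentence to Section IX saying that the pooled primary comparison is tested at two-sided 0.05 and that the one-sided 20% figure is illustrative. Section III (Procedures and Materials) says "we, as the study team, are also currently blinded to dose assignments until the end of the intervention period for all participants". If that still holds when the sentence is written, the team can settle it without knowing results by arm.

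**Cost:** a few sentences and no loss of power. The more favourable one-sided figure can no longer be used for the decision.

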**UCM Laboratory Abnormality Referral Algorithm**

[figure not shown]
Abnormal results emailed / paged to research coordination team for follow-up:

\*Study investigator on call after hours to facilitate emergent ER referrals. Will take critical value pages from lab when research team unavailable.

[figure not shown]
## Rush Laboratory Abnormality Referral Algorithm

Abnormal results emailed / paged to research coordination team for follow-up:

## PTH Referral Algorithm- UCM and Rush Laboratory Abnormality Referral Algorithm

Abnormal results emailed / paged to research coordination team for follow-up:

## XII. Data and Safety Monitoring Board (DSMB) Charter

### Trial Monitoring

The trial will be monitored by an independent Data and Safety Monitoring Board for this study made up of three members of the UC BSD faculty with experience in clinical trial management and expertise in critical care, pulmonology, and biostatistics. The DSMB members are: [name], DSMB Chair, [name], and [name].

### Monitoring Frequency

The DSMB will meet to review initial laboratory values and quarterly thereafter to review the overall protocol administration, review adverse events, and trends in laboratory values for determination of safe progression of the study. DSMB members will schedule additional meetings as needed to review adverse events. In addition to these quarterly meetings, Board members, along with the PI and Co-Investigators, will receive regular data reports from phlebotomy with all subjects' laboratory values, with higher values indicated. Board members will keep in close contact with the PI and Co-Investigators to refer individual patients to seek outside care for high laboratory values, in addition to the resources provided to subjects to seek care, such as an on-call pager for primary care.

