### Dose, Frequency, and Administration of the Intervention

Subjects will receive one bottle of a 9-month supply of a vitamin D dose depending on the arm they are randomized to and contingent on their preference for moderate vs. high vitamin D dose. At the end of the study, subjects will be asked to discard any remaining pills in their bottle given that some subjects participate for 3-6 months of follow-up if recruited after October 1, 2022. A low-dose treatment arm (400 IU) will be compared with those in the moderate (4,000 IU/day) to high (10,000 IU/day) treatment arm. Subjects will retrieve blinded bottles containing a 9-month supply of vitamin D at the DCAM pharmacy if they live or work closer to UCM, and at the Rush University Professional Office building, [name] if they live or work closer to Rush. In the event subjects are unable to pick up their vitamin D bottles in these physical locations, bottles will be mailed to an address they provide. The source of the intervention will be the University of Chicago Investigational Drug Service where the bottles will be distributed to DCAM and [name]'s lab at Rush.

**1) Dosing.** The proposed trial will compare high dose (10,000 IU/d) or moderate dose (4,000 IU/d) to low dose (400 IU/d) vitamin D as opposed to lower doses, e.g., 2,000 IU/d maximum dose in the Harvard trial. Schwartz et al. (left panel below) show that 800 or 2000 IU/d produce average levels of only about 35 ng/ml compared to 40-45 ng/ml for 4000 IU/d and 55 ng/ml for 50,000 IU/week. Data from McCullough et al. (Panel A, B below) shows that long-term administration of 10,000 IU/d produces much higher steady state vitamin D levels (about 95 ng/ml) compared to 5000 IU/d, producing about 60 ng/ml. Given the data discussed above on uncertainty about the optimal vitamin D intake/levels for immune function, this innovation in our proposed trial is potentially highly significant.

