### Procedures and Materials

Blood labs will be taken from subjects at intake, 3 months, 6 months and, if in the 9-month cohort, 9 months. If subjects are in the 2023 cohort (defined as recruited on or after January 1, 2023) blood labs will be taken from

subjects at intake, 3 months, and, if they are recruited in January or February 2023, they will have one final blood draw in June 2023. Labs for UCM subjects will be drawn at DCAM phlebotomy, River East phlebotomy, or Ingalls Hospital, depending on the location most convenient for the subject. Labs for Rush subjects will be drawn by [name] at his Rush lab.

Intake labs will measure baseline calcium and PTH levels, presence of COVID-19 antibodies, baseline vitamin D levels, and vitamin A levels. Where possible given constraints related to sample storage, analysis and available funding for free vitamin D measurement, vitamin D measurements will include free vitamin D levels measured by ELISA assay, as well as total vitamin D levels.

For Aim 7, Intake labs for UCM subjects will additionally measure vitamin D-binding protein (DBP), RAS components (Renin, Ang II, soluble ACE and ACE2), bradykinin, inflammation markers (IL-6, TNF- $\alpha$ , IL-1 $\beta$  and CRP), and SARS-CoV-2 antibodies against S-protein and N-protein.

Follow-up labs (excluding the final lab) will measure PTH levels, calcium levels, vitamin A levels for those who have high baseline vitamin A, and vitamin D levels for monitoring of the intervention's safety and outcomes, and COVID-19 antibodies for monitoring of the outcome. Records of these levels will be kept by the UCM and RU PIs and laboratories.

Final labs will measure calcium levels, vitamin D levels for monitoring of the intervention's safety and outcomes, and COVID-19 antibodies for monitoring of the outcome. Records of these levels will be kept by the UCM and RU PIs and laboratories. Final labs will not measure PTH levels. During the intervention period, our study monitors PTH levels for active participants, because primary hyperparathyroidism is a risk factor for vitamin D toxicity. Given that participants will no longer be taking study-provided vitamin D after their final lab draw, we do not believe it is medically necessary or an appropriate use of limited study resources to continue checking PTH levels with this final draw.

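### Investigators and staff routinely see follow-up vitamin D levels, which would often reveal the arm in the low-versus-high comparison of a trial described as double-blind

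*Combined protocol and SAP*

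**What the plan says.** **Access.** Monitoring Frequency in Section XII states: "Board members, along with the PI and Co-Investigators, will receive regular data reports from phlebotomy". The same sentence gives the scope of the reports: the recipients "will receive regular data reports from phlebotomy with all subjects' laboratory values, with higher values indicated". Section III, Procedures and Materials, says separately: "Laboratory records will be monitored regularly by site PIs, Co-Investigators, and members of the DSMB and Clinical Advisory Committee for safety". The same section has study staff maintaining and monitoring the laboratory records, and Section XI has study analysts working with the PI and co-investigators to pass laboratory data to the DSMB.

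**Content.** Procedures and Materials lists, for both the follow-up and the final draws, "vitamin D levels for monitoring of the intervention's safety and outcomes, and COVID-19 antibodies for monitoring of the outcome". It adds: "Records of these levels will be kept by the UCM and RU PIs and laboratories".

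**Blinding.** The Section III Summary and Section VII call the trial double-blinded. Procedures and Materials states that "we, as the study team, are also currently blinded to dose assignments until the end of the intervention period for all participants". The only withholding of levels that the documents describe is from subjects (Procedures and Materials; Section XIV).

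**Expected levels.** The Dosing paragraph of Section III gives about 35 ng/ml for 800 or 2,000 IU/d, 40-45 ng/ml for 4,000 IU/d, 55 ng/ml for 50,000 IU/week, about 60 ng/ml for 5,000 IU/d and about 95 ng/ml for 10,000 IU/d, the last as a long-term steady state. It gives no level for the 400 IU/d control and no SDs.

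**The concern.** Post-randomization vitamin D is a direct marker of the dose taken. Each subject's choice of randomization (low versus high, or low versus moderate) is recorded on the consent form (Section XIV). For a subject in the low-versus-high stratum, the only unknown is therefore 400 versus 10,000 IU/d, and the level bears directly on it.

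Three activities involve judgment and could be influenced by knowing the arm:

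- **Record review.** Medical records are reviewed for COVID-19 and its severity, and no masked reviewer is specified.
- **Staff contact.** Staff remind subjects about surveys and laboratory visits, and some surveys are completed by telephone.
- **Analysis choices.** Section IX leaves the covariate list open, allows visual assessment of Schoenfeld residuals, and does not specify the non-proportional hazards models.

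Even without bias, a report that called the low-versus-high comparison double-blind without qualification would be hard to defend.

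**Working it through.** The plan states no figure on this point, so there is nothing to reproduce. The check has two parts.

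**1. Does any text block the flow of information?** Monitoring Frequency covers all subjects on a regular basis, so it is not a system of safety alerts only. It does not name vitamin D. That link comes from Procedures and Materials, which includes vitamin D in every follow-up and final draw and independently gives site PIs and co-investigators regular access to laboratory records. No section removes vitamin D from these reports, masks subject identifiers, or confines individual levels to an unblinded reviewer.

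**2. How well does one level separate the arms?** Assume 1:1 allocation within the stratum, normal levels with a common SD, and a cut midway between the arm means. Then

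share correctly classified = Φ((m1 − m0) / (2 × SD)).

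Guessing gives 50%. The control mean m0 is set at 35 ng/ml, the protocol's figure for 800 or 2,000 IU/d. Both doses exceed 400 IU/d, so this probably understates the separation. The SD is assumed, because the documents give none.

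| Contrast | SD 15 | SD 20 | SD 25 |
|---|---|---|---|
| High at 95 vs 35 | Φ(30/15) = 97.7% | Φ(30/20) = 93.3% | Φ(30/25) = 88.5% |
| High at 55 vs 35 | Φ(10/15) = 74.8% | Φ(10/20) = 69.1% | Φ(10/25) = 65.5% |
| Moderate at 42.5 vs 35 | Φ(3.75/15) = 59.9% | Φ(3.75/20) = 57.4% | Φ(3.75/25) = 56.0% |

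The 55 ng/ml row is a deliberately low case. It is the protocol's figure for 50,000 / 7 ≈ 7,143 IU/d, and the same paragraph reports about 60 ng/ml on 5,000 IU/d.

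**Sensitivity, using the best single cut in place of the midpoint:**

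- *Unequal SDs, 95 vs 35.* From 8 (low arm) and 10 (high arm) up to 15 and 30: 91.5% to 100%.
- *High-arm mean of 55, control mean 25 to 35, same SD range.* 71% to 95%.
- *Non-adherence, 95 vs 35, SDs 12 and 25, cut at 58.* With a fraction q of the high arm at low-arm levels, the share is 0.5 × Φ(23/12) + 0.5 × [(1 − q) × Φ(37/25) + q × (1 − Φ(23/12))]. At q = 0.20 this is 0.5 × 0.972 + 0.5 × (0.8 × 0.931 + 0.2 × 0.028) = 86%. At q = 0.40 it is 77%.
- *Moderate 40-45 vs control, SDs 8 to 15.* 57% to 73% with a control mean of 35. It reaches 89% only at the extreme of a control mean of 25, a moderate mean of 45 and SD 8.

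**The case against.** **The allocation is not disclosed.** A reader might infer that the plan hands investigators the dose assignments and so flatly contradicts itself. It does not. The blinding statement concerns assignments, and no section releases the list. What the text permits is inference from a biomarker.

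**One result does not identify nearly everyone.** A reader might infer this from 95 versus 35 ng/ml, but 95 is a long-term steady-state figure. Draws start at 3 months, and March 2023 enrollees have only one follow-up draw. Adherence will be imperfect, and entry levels up to 100 ng/mL are allowed. Against that, most subjects have repeated draws and investigators also hold the baseline value. The objection stands as a limit on certainty.

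**Bias in the primary result is not shown.** The primary outcome is the subject's own report of clinically confirmed COVID-19, or PCR when available. Subjects are blinded to dose and levels, seek PCR outside the study, and usually answer by web. Seroconversion is a laboratory assay, and hospitalization, ICU stay, ventilation and death leave limited discretion. This stands and lowers the stakes.

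**Overlap of roles is inferred.** Record reviewers are not named. Reminders come from coordinators and analysts, while the regular reports go to the DSMB, PI and co-investigators. Study staff do monitor laboratory records, so overlap is possible but not established.

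**Some of the exposed work follows planned unblinding.** The team's blinding lasts only until the intervention ends for all participants, June 2023 under the extended timeline. Pursuit of overdue surveys beyond 30 June 2023, much of the later enrollees' 12-month chart review, and some final analysis come after that. Masking vitamin D alone would not protect those steps, so the remedy must also address dose assignment.

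**The affected share is unknown.** Subjects choose their stratum, and the documents do not say how many choose low versus high.

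**Conclusion.** The concern holds as functional unblinding of the low-versus-high stratum. Routine access to individual follow-up vitamin D is written into the plan, no masking is described, and the plan nevertheless claims a double-blind trial with a blinded team.

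On the protocol's own means and an assumed SD of 15 to 25 ng/ml, one level would classify about 88% to 98% of that stratum correctly at steady state. The figure is about 69% to 75% (SD 15 to 20) if the high-arm mean were only 55 ng/ml, and non-adherence lowers it in either case. Low versus moderate is much less exposed on the protocol's figures.

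The risk lies in staff follow-up contacts, record review for COVID-19 and severity, and analysis decisions made before planned unblinding. The documents do not support a claim that the primary comparison is biased. The plan should be changed because the protection is cheap and the blinding statement would otherwise be inaccurate for this stratum.

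**What to change.** 1. In Procedures and Materials and in Monitoring Frequency, limit numeric post-randomization vitamin D values to the DSMB, or to a designated unblinded safety reviewer, until planned unblinding. Align the statements on record keeping, staff access and the Section XI data route, which now runs through study analysts and the PI. Section V has the Rush site PI collecting samples, so set out the Rush result route explicitly.
2. Investigators and coordinators keep calcium, PTH, baseline vitamin D, and a flag when a follow-up vitamin D value crosses a limit the protocol already states (exclusion criterion 13 gives one). Baseline values must stay visible because eligibility with raised PTH depends on them.
3. State that record review and final analysis choices are made without access to follow-up vitamin D or dose assignment, and that the analysis choices are fixed before unblinding. The planned time-varying vitamin D analyses can then use the levels after unblinding.
4. If investigator access is kept, correct the double-blind and blinded-team statements for the low-versus-high stratum.

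**Cost.** Changes to laboratory report content and data permissions, plus a wording amendment. The calcium referral tiers in Sections X and XI are unaffected. Investigators would see a numeric follow-up vitamin D value only when it is flagged. The referral algorithm figures in Section XI are not reproduced in the text reviewed, so the change should be checked against them before adoption.
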